7.1.5.1. Statistical Methodology Specification

| |
|---|
| Endpoint / Variables |
| 
 • Mean change in Hgb between baseline and over the evaluation period (EP, mean over Weeks 24 to 28) |
| Model Specification |
| 
 • The EP Hgb value will be defined as the mean of all available Hgb values (on and off-treatment) during the EP (Week 24 to Week 28 inclusive) • The ANCOVA model used to quantify the difference in mean Hgb change will adjust for the following baseline values: 
 ○ Treatment ○ Baseline Hgb (see Section 5.2) ○ Region (as randomized, see Section 5.3 & Section 5.4) |
| Multiple Imputation Analysis |
| 
 • Multiple imputation analysis will be performed using all available Hgb values (on and off-treatment) and conducted under a set of assumptions about missing Hgb values (see Section 10.6.3). 
 ○ For each of the missing dataset (out of the 200 imputed as indicated above), the missing scheduled Hgb values through Week 28 will be imputed based on the MNAR assumption and will be performed using PROC MI. The regression will have region, treatment, baseline Hgb, off treatment status, prior scheduled (possibly imputed) Hgb values as covariates (see Model Checking & Diagnostics, below). The seed for reproducibility is set to 205270. ○ Missing data will be considered MNAR and classified as either being on-treatment or off-treatment, with the former being imputed with only on-treatment data and the latter being imputed with only off-treatment data 
 ▪ Subsequent missing data will be classified as being on-treatment, if 
 • Patients who die, use non-randomized ESA Medication, Receipt of Blood Transfusions while on treatment • Study Drug Interruption (e.g. temporarily stopped trt due to COVID, then restarted) ▪ Subsequent missing data will be classified as being off-treatment, if 
 • Treatment discontinuation • Patients who die, use non-randomized ESA Medication, Receipt of Blood Transfusions after treatment discontinuation |

CONFIDENTIAL

205270

- The low and high cutoffs at Hgb values of 6 g/dL and 15 g/dL will be applied to all imputed Hgb values.

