- EP Hgb values will be computed and compared across treatment groups using the co-primary ANCOVA model described above. Rubin's rules [Rubin, 1987] will be used to combine results of the imputed datasets using SAS PROC MIANALYZE procedure. As a result, a single estimated treatment difference and its standard error will be produced, with which a 95% CI will be calculated.

Model Checking & Diagnostics

- Distributional assumptions underlying the model used for analysis will be examined by obtaining a normal probability plot of the residuals and a plot of the residuals versus the fitted values (i.e. checking the normality assumption and constant variance assumption of the model respectively) to gain confidence that the model assumptions are reasonable.
- If there are any departures from the distributional assumptions, alternative models will be explored using appropriate transformed data.
- Models will be examined for treatment interactions with baseline Hgb and stratification factor
- Missing data imputation:
 - When imputing for each of the missing dataset (out of the 200), if there are error and or warning messages related to the by statement and/or regression model (e.g. not enough observations with the statement), try impute with randomized treatment, baseline Hgb, treatment status, prior scheduled (possibly imputed) Hgb values and region as covariates.
 - If there are no observed off-treatment Hgb values at a visit, the missing Hgb values at that visit will be imputed based on only the observed on-treatment Hgb values.

Model Results Presentation

- All available observed Hgb values (on and off-treatment) will be summarized using mean, standard deviation, minimum, P25, median, P75 and maximum at each visit by treatment group. In addition to scheduled visits, the baseline value and mean EP will be included (see Section 10.6.3). The summaries described above will be produced using the analysis defined Hgb.
 - This display will be repeated for visits up to and including Week 28, using the data used for the primary Hgb analysis (i.e., including imputed values).
- All available observed Hgb change from baseline values (on and off-treatment) will also be summarized using mean, standard deviation, minimum, P25, median, P75, and maximum at each post-baseline visit, including the mean EP (see Section 10.6.3).

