 - This display will be repeated for visits up to and including Week 28, using the data used for the primary Hgb analysis (i.e., including imputed values).
- The number and percentage of subjects with imputed data in the primary Hgb analysis will be provided by treatment group. The number and percentage of subjects by reason for data imputation will be provided. Reasons include: death before Week 24, death during Week 24 – 28, investigator site closed before Week 24, investigator site closed during Weeks 24-28, lost to follow-up before Week 24, lost to follow-up during Week 24 – 28, consent withdrawn before Week 24, consent withdrawn during Week 24 – 28, and other monotone missing Hgb values. Subjects will be further classified as either having observed both scheduled EP Hgb values, Having observed a partial schedule of EP Hgb values, having observed no scheduled EP Hgb values with at least one unscheduled EP Hgb value, or having observed no EP Hgb values, scheduled or unscheduled. For subjects with partial scheduled EP Hgb values, the amount of imputed data (1 scheduled Hgb values missing) will be summarized. For subjects with partial scheduled EP Hgb values and a monotone imputed data pattern, the reason for the monotone imputed scheduled EP Hgb values will be provided. Reasons include: death during Week 24-28, investigator site closed during Weeks 24-28, lost to follow-up during Week 24 – 28, consent withdrawn during Week 24 – 28, and other monotone imputed Hgb values. And for summaries of the amount of missing scheduled EP Hgb values, the presence or absence of additional unscheduled EP Hgb values will be summarized.

CONFIDENTIAL

205270

- The least square (LS) mean estimates and standard errors by treatment group, LS mean difference, two-sided 95% CI and one-sided superiority p-value for the difference in the primary Hgb endpoint between the daprodustat and placebo arms from the ANCOVA model will be presented. The number of subjects contributing to the analysis and the associated mean and standard deviation of the baseline and EP Hgb values will also be displayed with the results of the ANCOVA model.

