- All available mean Hgb values (on and off-treatment) will be displayed graphically for each scheduled study visit using a line plot. The line plot of mean values and the 95% CI by time will include horizontal reference lines to depict the hemoglobin analysis range (11-12 g/dL), vertical reference lines to identify the EP (weeks 24-28), and the number of subjects by treatment group contributing to each mean value.
- All available Hgb change from baseline values (on and off-treatment) will be displayed graphically for each scheduled study visit using a line plot. The line plot of mean values and the 95% CI by time will include vertical reference lines to identify the EP (Weeks 24-28), and the number of subjects by treatment group contributing to each mean value.
- A listing of all hemoglobin values will be provided, including treatment, site ID, unique subject ID, subject ID, visit, assessment date, select demographic information and central laboratory and HemoCue Hgb values.

Model Results Interpretation

Superiority will be established if the one-sided p-value is less than 0.025.

Subgroup Analyses

- Subgroup analysis will be performed using all available Hgb values (on and off-treatment) and separately using evaluable Hgb values only (see Section 10.6.3).
- Subgroup analysis details are discussed in Section 5.4.
- The ANCOVA model used to quantify the difference in mean Hgb change will adjust for the following baseline values:
 - Treatment
 - Baseline Hgb (see Section 5.2)
 - Region (as randomized, see Section 5.3 & Section 5.4)
 - Subgroup
 - Subgroup * treatment interaction term

Supportive Analyses

- A supportive analysis using while alive and on treatment strategy (on-drug analysis) will be considered. In this analysis, the EP Hgb will be determined using evaluable Hgb values (Section 10.6.3). Hgb values collected after IP discontinuation, or within 8 weeks following a red blood cell transfusion, a whole blood transfusion, or a nonrandomized ESA treatment would be irrelevant to the analysis, since they are not of interest in this estimand.

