10.6.3. Efficacy

| Hemoglobin Values |
|--|
| Central Laboratory and HemoCue Hgb Values |
| 
 • When source of Hgb measurement is not specified: 
 ○ For reporting purposes, central laboratory Hgb values will be used, unless otherwise specified. However, if a central laboratory Hgb value is missing, a corresponding non-missing HemoCue Hgb value will be used. • Multiple HemoCue Hgb values at a single visit: 
 ○ The dose adjustment algorithm will require sites to obtain two HemoCue Hgb values at some visits. In the case where two HemoCue Hgb values are obtained at a visit, the average of the two measurements, which will be rounded to the nearest 10th decimal place, should be used as the HemoCue Hgb value for that visit. |

CONFIDENTIAL

205270

| |
|---|
| Hemoglobin Values |
| Evaluable Hemoglobin Values |
| 
 Evaluable Hgb values are on-treatment Hgb values (see Section 10.4.1) that are not taken within the 8 weeks following a red blood cell transfusion, a whole blood transfusion, or a nonrandomized ESA treatment which occurs on or after the randomization date. |
| Evaluation Period (EP) Hemoglobin Value for Primary Hgb Analysis |
| 
 For each participant, the mean of all available (on and off treatment) Hgb values for Week 24 through Week 28, inclusive, including any unscheduled Hgb values that were taken during this time period. |
| Evaluation Period (EP) Hemoglobin Value for On-drug Hgb Supportive Analysis |
| 
 For each participant, the mean of all evaluable Hgb values for Week 24 through Week 28, inclusive, including any unscheduled Hgb values that were taken during this time period. |
| Imputed Hemoglobin Values |
| 
 For each missing value between baseline to Week 28 (inclusive), 200 imputed values will be generated using the multiple imputation method (see Section 7.1.2). The average of these 200 imputed values will be used as the value for this missing value in the summary tables and figures. For the primary efficacy Hgb analysis and the corresponding subgroup analyses using all available observed and imputed Hgb values (on and off-treatment), Rubin's rules [Rubin, 1987] will be used to combine results of the imputed datasets using SAS PROC MIANALYZE procedure. |
| Time In Range |
| Time in Range During the EP |

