10.10.7. Efficacy Figures

| Efficacy: Figures | | | | | |
|---|------------|----------------------|--|---------------------------------------|-------------|
| No. | Population | IDSL / Example Shell | Title | Programming Notes | Deliverable |
| Primary Efficacy Analyses: Model based Mean Change in Hgb between Baseline and Evaluation Period | | | | | |
| 2.1. | ITT | EFF_F1 | Line Plot of Post-randomization Observed and Imputed Hemoglobin Data by Visit | | DR, SAC |
| 2.2. | ITT | EFF_F1 | Line Plot of Post-randomization Observed and Imputed Hemoglobin Change from Baseline | | DR, SAC |
| Principal Secondary Efficacy Analyses | | | | | |
| 2.3. | ITT | EFF_F1 | Line Plot of On-Treatment Observed and Imputed SF-36 vitality sub-score values by Visit, Traditional Scoring | | DR, SAC |
| 2.4. | ITT | EFF_F1 | Line Plot of On-Treatment Observed and Imputed SF-36 vitality sub-score values Change from Baseline | | DR, SAC |
| Secondary Efficacy Statistical Analyses: Symptom Severity and Change | | | | | |
| 2.5. | ITT | EFF_F3 | Bar Chart of On-treatment Baseline and CKD-AQ Domain and Single Item Scores by Visit | Page by domain and single item scores | DR, SAC |
| 2.6. | ITT | EFF_F4 | Stacked Bar Chart of On-treatment Baseline and Week 28 Scores for PGI-S Response | | DR, SAC |
| Secondary Efficacy Statistical Analyses: HRQoL and Utility score | | | | | |
| 2.7. | ITT | EFF_F3 | Bar Chart of On-treatment SF-36 individual items of the Vitality Domain Scores Change from Baseline | Page by individual items | DR, SAC |
| 2.8. | ITT | EFF_F3 | Line Plot of On-treatment SF-36 Physical Function Domain Scores Change from Baseline | | SAC |

CONFIDENTIAL

205270

| Efficacy: Figures | | | | | |
|---|------------|----------------------|---|-------------------|-------------|
| No. | Population | IDSL / Example Shell | Title | Programming Notes | Deliverable |
| 2.9. | ITT | EFF_F3 | Bar Chart of On-treatment EQ-5D-5L Scores by Visit | | DR, SAC |
| Exploratory Efficacy Statistical Analyses: Iron Parameters | | | | | |
| 2.10. | ITT | EFF_F1 | Line Plot of On-treatment Hepcidin Data by Visit | | DR, SAC |
| 2.11. | ITT | EFF_F1 | Line Plot of On-treatment Hepcidin Percent Change from Baseline | | DR, SAC |
| 2.12. | ITT | EFF_F1 | Line Plot of On-treatment TSAT Data by Visit | | DR, SAC |
| 2.13. | ITT | EFF_F1 | Line Plot of On-treatment TSAT Change from Baseline | | DR, SAC |
| 2.14. | ITT | EFF_F1 | Line Plot of On-treatment Ferritin Data by Visit | | DR, SAC |

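### Entering the average of 200 imputations as one value makes the SDs in the observed-and-imputed Hgb displays too small, and their 95% CIs too narrow if imputed values are plotted (minor, descriptive only)

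*SAP*

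**What the plan says.** SAP section 10.6.3, under imputed hemoglobin values, generates 200 imputations for each missing Hgb value up to Week 28. It then rules on displays: "The average of these 200 imputed values will be used as the value for this missing value in the summary tables and figures". The next bullet assigns Rubin's rules to the primary Hgb analysis and its subgroup analyses. Nothing assigns them to the displays.

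Section 7.1.5.1 asks for by-visit summaries (mean, SD, minimum, quartiles, maximum) of Hgb and of change from baseline. It asks for each to be repeated "using the data used for the primary Hgb analysis (i.e., including imputed values"). The list of displays carries these as Tables 2.3 and 2.4, with Table 2.8 by subgroup. Tables 2.1, 2.2 and 2.7 are the observed-only counterparts, and Table 2.5 reports how much was imputed.

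For the figures, section 7.1.5.1 says: "All available mean Hgb values (on and off-treatment) will be displayed graphically for each scheduled study visit using a line plot". It adds: "The line plot of mean values and the 95% CI by time will include horizontal reference lines". It does not mention imputed data there. Section 10.10.7 titles Figure 2.1 "Line Plot of Post-randomization Observed and Imputed Hemoglobin Data by Visit" and Figure 2.2 "Line Plot of Post-randomization Observed and Imputed Hemoglobin Change from Baseline".

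For the table of the primary result (Table 2.6), section 7.1.5.1 states that "the associated mean and standard deviation of the baseline and EP Hgb values will also be displayed with the results of the ANCOVA model". It does not say how imputed values enter that SD.

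Section 10.6.3 refers to section 7.1.2 for the imputation method. Section 7.1.2 is the summary measure; the method is in 7.1.5.1.

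**The concern.** Each imputed draw has two parts: a predicted value and a random residual that restores the natural spread. Averaging 200 draws removes nearly all of the residual. Participants with observed values keep their full variance and imputed participants do not, so an SD over the mixture is too small. A CI computed from that SD and the full number of participants has a second fault: it treats imputed values as if they had been measured and leaves out the between-imputation variance.

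The rule also does not do what the tables are for. They are meant to show the data behind the primary analysis. That analysis uses 200 completed datasets, and one dataset of averaged values is not the same thing.

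At stake is the description of spread in the Hgb displays that cover every randomized participant. No test or decision depends on it.

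**Working it through.** **Inputs.** From protocol section 10.2.1: 600 randomized, up to 10% withdrawing before Week 24, at least 540 evaluable, SD 1.5 g/dL for Hgb change from baseline to the evaluation period (EP). These reproduce: 600 × 0.90 = 540, and the smallest significant difference is 1.96 × 1.5 × √(2/270) = 0.253, against the stated 0.25 g/dL. The documents give no figure for the precision of the imputed displays.

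**Assumptions.** Missing fraction m = 0.10, using the withdrawal ceiling as a proxy; earlier visits should have less. Imputation R² is not given. The model is described only by its predictors: "The regression will have region, treatment, baseline Hgb, off treatment status, prior scheduled (possibly imputed) Hgb values as covariates". R² is therefore varied. R² = 0 is shown only as a theoretical bound, because prior Hgb values are predictors.

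**Formulas**, in units of the true variance, for many imputations and no mean shift:
- Variance displayed after averaging: 1 − m(1 − R²). SD ratio = √[1 − m(1 − R²)].
- Rubin variance of a visit mean, times n: 1 + m(1 − R²)/(1 − m).
- CI ratio = √{[1 − m(1 − R²)] / [1 + m(1 − R²)/(1 − m)]}.

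Example, R² = 0.5: displayed variance 1 − 0.10 × 0.5 = 0.95, so SD ratio √0.95 = 0.975. Rubin term 1 + 0.05/0.90 = 1.0556, so CI ratio √(0.95/1.0556) = 0.949.

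| R² | SD low, 10% missing | CI narrow, 10% missing | SD low, 5% missing | CI narrow, 5% missing |
|---|---|---|---|---|
| 0 (bound) | 5.1% | 10.0% | 2.5% | 5.0% |
| 0.25 | 3.8% | 7.6% | 1.9% | 3.8% |
| 0.5 | 2.5% | 5.1% | 1.3% | 2.5% |
| 0.8 | 1.0% | 2.1% | 0.5% | 1.0% |
| 0.9 | 0.5% | 1.0% | 0.3% | 0.5% |

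A simulation (regression imputation with parameter draws, 200 imputations, 300 per arm, 10% missing, 400 replicates) gave SD 5.1, 2.5 and 1.0% low and CI 10.0, 5.1 and 2.1% narrow at R² 0, 0.5 and 0.8. This agrees with the formulas.

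**Mean shift.** Off-treatment missing values are imputed from off-treatment data only, so imputed values may sit away from the observed mean. A shift of d SDs adds m(1 − m)d² to both variances. For 1 g/dL, d = 1/1.5 and the addition is 0.09 × 0.444 = 0.04. At R² 0.25, 0.5 and 0.8 the SD ratios are √(0.965/1.04), √(0.99/1.04) and √(1.02/1.04), or 3.7, 2.4 and 1.0% low. The SD shortfall hardly moves.

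**Quartiles** behave differently. IQR from the quantiles of a two-part normal mixture, 10% missing:

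| Downward shift | R² 0.25 | R² 0.5 |
|---|---|---|
| none | 7.4% narrower | 3.6% narrower |
| 0.75 g/dL (0.5 SD) | 4.6% narrower | 2.6% narrower |
| 1.5 g/dL (1 SD) | 0.4% wider | 0.3% narrower |
| 2 g/dL | 2.9% wider | 1.1% wider |

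**Absolute size**, illustrative only, because the 1.5 g/dL is stated for change to the EP and not for by-visit levels. With 300 per arm, 1.96 × 1.5/√300 = 0.170 g/dL. At R² = 0.5 the averaged half-width is 0.170 × √0.95 = 0.165 and the pooled one 0.170 × √1.0556 = 0.174, a gap of 0.009 g/dL. At R² = 0.25 the gap is 0.013, and at R² = 0.8 it is 0.004.

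**The case against.** The strongest reply is that nothing depends on these displays. Inference uses Rubin's rules, the observed-only tables show the actual spread, and Table 2.5 tells the reader how much was imputed. That stands, and it is why the point is minor. It does not make the stated rule right for the tables to which it applies.

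Second, 10% is a planning ceiling. Earlier visits should have less missing data, and a HemoCue value replaces a missing central-laboratory value before any imputation. With serial Hgb as predictors, R² may be high. At 5% missing and R² of 0.8 the effect is 0.5% on the SD and 1.0% on the CI. This also stands as a statement about size.

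Third, the CI point is conditional. Section 7.1.5.1 describes the line plots in terms of available values, and neither it nor the figure list says how the CI is computed. The firm finding on the figures is that text and titles disagree.

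A reader might infer that quartile ranges are always too narrow. They are not: with a large shift the IQR can be too wide. A reader might also infer that the EP SD in Table 2.6 is wrong. The SAP is silent on whether the averaging rule applies there, so what is needed is clarification.

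**Conclusion.** The rule in section 10.6.3 understates the SDs in Tables 2.3, 2.4 and 2.8. At an assumed 10% missing and R² from 0.25 to 0.9 the shortfall is 3.8% down to 0.5%. If Figures 2.1 and 2.2 use the averaged values and an ordinary CI, the error bars are 7.6% down to 1.0% too narrow. The 5.1% and 10.0% at R² = 0 are a bound and not an expectation. Quartiles are distorted: the IQR is narrower with no or modest shift and can be slightly wider with a shift of about 1.5 to 2 g/dL or more.

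It would be tempting to conclude that the primary CI or p-value is too favourable. The documents do not support that: the primary and subgroup ANCOVA pool by Rubin's rules. Displayed means are essentially unchanged, and Tables 2.1, 2.2 and 2.7 are unaffected. This is a minor descriptive error with no effect on the primary conclusion. The existence of the SD shortfall is certain from the rule; its size rests on the assumed missing fraction and R².

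**What to change.** Replace the averaging sentence in SAP section 10.6.3 with: *For tables and figures based on observed and imputed Hgb, each statistic is computed in each of the 200 completed datasets. The mean and its 95% CI are combined by Rubin's rules. The SD is the square root of the average within-dataset variance. P25, median and P75 are averaged across datasets. Minimum and maximum are taken from observed data.*

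Three further edits:
- Reconcile the description of the line plots in section 7.1.5.1 with the titles of Figures 2.1 and 2.2, and state which data are plotted.
- State that the same rule covers any EP SD in Table 2.6 that includes imputed data.
- Correct the cross-reference in section 10.6.3 from 7.1.2 to 7.1.5.1.

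The cost is SAP wording and modest programming, because the 200 datasets already exist. Displayed SDs, and any error bars based on imputed data, become slightly wider. The primary result does not change.

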7.1.4. Strategy for Intercurrent (Post-Randomization) Events

The following are the intercurrent events for the primary efficacy analyses:

- Death prior to the end of the EP (i.e. before Week 28 visit)
- Randomized treatment discontinuation prior to the end of the EP
- Use of non-randomized ESA medications for any reason including rescue prior to the end of the EP
- Receipt of blood transfusions prior to the end of the EP

Except for the intercurrent event of deaths prior to the end of the EP, a treatment policy strategy will be used in which all scheduled Hgb data recorded during the EP (Weeks 24-28) will be included in the primary efficacy analysis, regardless of discontinuation of study medication due to any reasons, and regardless of receipt of non-randomized ESA medications for any reason including rescue, or blood transfusions. For deaths, a hypothetical strategy will be used as described in Section [7.1.5.1](#).

The following are causes of missing Hgb data affecting the primary efficacy endpoint that are not due to intercurrent events:

- Study withdrawal prior to the end of the EP
- Permanent switching from clinic visits to remote visits prior to start to EP
- Intermittent missing Hgb values at one or more visits with the EP

Missing data will be imputed as described in Section 7.1.5.1.

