| 
 Number of days that a participant's Hgb is within the analysis range of 11-12 g/dL, or ≥ 13 g/dL, or increase of ≥ 1.0 g/dL from baseline inclusive for Week 24 through Week 28 inclusive, including any unscheduled evaluable Hgb values. If Hgb is missing, linear interpolation is used to estimate Hgb between visits, accounting for any intermittent missing values (Rosendaal, 1993). |
| Percent Time in Range During the EP |
| 
 Time in Range During the EP / [Earlier of (Treatment Stop Date, Week 28 visit date) – Week 24 visit date + 1] Note: Percent time in/below/above range during the EP is only defined for subjects with a Treatment Stop Date that is on or after their Week 24 visit date, and have at least two evaluable Hgb values on different days, where at least one evaluable Hgb value is contained within the EP and another evaluable Hgb value occurs within the range of the Week 12 visit through Week 28 visit, inclusive. |
| Time in Range During the Treatment Period |
| 
 Number of days that a participant's Hgb is within the analysis range of 11-12 g/dL, or ≥ 13 g/dL, or increase of ≥ 1.0 g/dL from baseline inclusive for Day 1 through Week 28 inclusive, including any unscheduled evaluable Hgb values. If Hgb is missing, linear interpolation is used to estimate Hgb between visits, accounting for any intermittent missing values (Rosendaal, 1993). |
| Percent Time in Range During the Treatment Period |
| 
 Time in Range During the Treatment Period / [Earlier of (Treatment Stop Date, Week 28 visit date) – Day 1 visit date + 1] |
| Time to Stopping Randomized Treatment Due to Meeting Rescue Criteria |
| Event Date |
| 
 Treatment stop date when the primary reason and subreason for randomized treatment stop are: 
 Primary reason: Participant reached protocol-defined stopping criteria |

CONFIDENTIAL

205270

| |
|---|
| Time to Stopping Randomized Treatment Due to Meeting Rescue Criteria |
| ○ Subreason: Rescue |
| General Definitions |

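### Percent time in range divides by on-treatment days after the last evaluable Hgb, which have no Hgb estimate, so every time-based percentage is understated for the participants affected

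*SAP*

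**What the plan says.** SAP 10.6.3 gives two percentages. For the EP it is "Time in Range During the EP / [Earlier of (Treatment Stop Date, Week 28 visit date"), less the Week 24 visit date, plus 1. For the treatment period it is "Time in Range During the Treatment Period / [Earlier of (Treatment Stop Date, Week 28 visit date) – Day 1 visit date + 1"]. The numerator is the number of days on which Hgb meets the condition (11 to 12 g/dL, at least 13 g/dL, or a rise of at least 1.0 g/dL). The same section adds: "If Hgb is missing, linear interpolation is used to estimate Hgb between visits, accounting for any intermittent missing values". It gives no rule for days before the first or after the last value.

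SAP 7.3.2.1 restricts the analysis to evaluable Hgb. SAP 10.6.3 defines these as on-treatment values "that are not taken within the 8 weeks following a red blood cell transfusion"; the same exclusion applies after whole blood or a non-randomized ESA. For Hgb, SAP 10.4.1.1 ends the on-treatment state one day after the Treatment Stop Date.

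The EP version has an entry condition: treatment must continue to the Week 24 visit or later, and two evaluable values must fall on separate dates. Their timing is also constrained: "where at least one evaluable Hgb value is contained within the EP and another evaluable Hgb value occurs within the range of the Week 12", with Week 28 as the upper limit. The treatment-period version has no minimum-data condition.

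Percent time in range is a listed secondary endpoint, tested by van Elteren for both periods (SAP 7.3.2.1). Percent time at or above 13 g/dL and with a rise of at least 1.0 g/dL are exploratory (SAP 7.4.2).

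**The concern.** The numerator and denominator cover different days. Interpolation needs a value on each side, so the numerator cannot grow after the last evaluable Hgb. The denominator continues to treatment stop or the Week 28 visit. A participant whose measured values are all in range can then score close to zero and fall to the bottom of the ranking used by the van Elteren test.

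The documents foresee several routes to this:
- The Week 28 Hgb is missing. SAP 7.1.4 names intermittent missing EP values among the causes of missing data.
- Treatment stops between visits. The discontinuation visit may be up to 2 weeks after stopping (Protocol Table 3), so its Hgb is often no longer on-treatment. Visits may be up to 5 weeks apart (Protocol 9).
- A transfusion or ESA outside the rescue pathway makes later on-treatment values non-evaluable.
- For the treatment period, "Permanent switching from clinic visits to remote visits prior to start to EP", if the participant is still taking drug.

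Two things are at stake. In-range time is understated mostly in the arm that reaches range. Time at or above 13 g/dL, a description of overshoot, is understated in whichever arm overshoots.

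**Working it through.** The plan states no figure for this endpoint, so there is none to reproduce. The Hgb profiles below are assumed, to show what the formulas do.

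**Day numbering.** Day = 1 + 7 × week: Week 4 = 29, Week 8 = 57, Week 20 = 141, Week 24 = 169, Week 26 = 183, Week 28 = 197.

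**EP, 11.5 g/dL at Weeks 20 and 24, no evaluable Week 28 value, treated to Week 28.** The entry condition is met.
- Denominator: 197 − 169 + 1 = 29 days.
- Days with an estimate inside the window: Day 169 only.
- As written: 1/29 = 3.4%. Below and above are both 0, so the three categories add to 3.4%.
- If treatment stops at Week 26 instead: 1/(183 − 169 + 1) = 1/15 = 6.7%.
- With an unscheduled 11.5 at Week 26 and treatment to Week 28: 15/29 = 51.7%, against 15/15 = 100% of covered days.

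**Control case: Weeks 20 and 28 present, Week 24 Hgb missing.** All 29 days are interpolated, giving 29/29 = 100%. Gaps between two evaluable values are handled correctly.

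**Treatment period, Hgb reaching 11.0 at Week 8, in range to a last value at Week 20, treated to Week 28.**
- Days in range: 141 − 57 + 1 = 85. Days below: 56.
- As written: 85/197 = 43%. Over measured days: 85/141 = 60%.
- Below + in + above: 141/197 = 71.6%.

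**Treatment period, 9.5, 10.5, then 11.5 g/dL from Week 8 to Week 24, no Week 28 value.** Interpolation reaches 11.0 on Day 43, so 169 − 43 + 1 = 127 days are in range. As written 127/197 = 64.5%; over covered days 127/169 = 75.1%.

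**At or above 13 g/dL: 9.5, 12.0 and 13.4 at Day 1, Week 4 and Week 8; treatment stopped on Day 84.** The line crosses 13.0 on Day 29 + 28 × (1.0/1.4) = 49, so 57 − 49 + 1 = 9 days qualify. As written 9/84 = 10.7%; over covered days 9/57 = 15.8%.

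**Effect on an arm mean (assumptions throughout).** I simulated 20,000 participants with true mean Hgb 11.3, between-participant SD 0.7 and visit SD 0.5. Mean EP time in range is about 45% with both EP values and about 1.5% when the Week 28 value is lost, a difference of 43.7 points. The arm mean falls by (fraction affected) × 43.7:

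| Fraction affected (assumed) | Fall in arm mean, points |
|---|---|
| 3% | 1.3 |
| 5% | 2.2 |
| 10% | 4.4 |

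**The case against.** The strongest reply is that the SAP never says days after the last value score zero. It counts days on which Hgb is in range and is silent on days it cannot estimate, so this could be called an unspecified rule. That is right about the wording. But the denominator is fully specified, and interpolation is the only stated way to fill a day. Code that follows the text gives 3.4%.

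A reader might infer that the untested days are reported as out of range. They are not: they enter neither the below-range nor the above-range count, so all the percentages are too low together.

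The routes are also narrower than they first look. HemoCue replaces a missing central value and unscheduled evaluable values count, so both sources must be absent at Week 28. Rescue requires permanent discontinuation, so a rescued participant's denominator already closes at treatment stop. Participants without any EP Hgb are excluded from the EP version. SAP 7.1.4 does not say that those on remote visits are still taking drug. These points reduce the number affected; they do not remove the fault.

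The consequence is limited. The test is nominal and outside the hierarchy. The in-range bias probably works against daprodustat. The counts of participants and of occasions at or above 13 g/dL do not use this denominator. The test is rank-based, so a shift in an arm mean does not convert directly into a change in its result, and no such change has been calculated.

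Multiple imputation is not an answer: it is specified for the primary Hgb analysis and carried to the first principal secondary endpoint, while time in range uses evaluable values only.

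**Conclusion.** The point holds. The stated denominator includes on-treatment days after the last evaluable Hgb, and every time-based percentage is understated for the participants concerned. For one participant the error can be large: 3.4% in the EP when every measured value is in range, or 43% against 60% over the treatment period. Across an arm the size is unknown, because the documents do not give the fraction affected; the falls of 1.3 to 4.4 points rest on assumed fractions and an assumed Hgb distribution.

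Two stronger readings should be resisted. The primary and principal secondary analyses do not use this derivation and are untouched. Nor does every missed visit distort the result, since gaps between evaluable values are interpolated correctly. This is a correction that should be made to a nominally tested secondary endpoint and to untested exploratory ones.

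**What to change.** In SAP 10.6.3:
1. End each denominator at the earlier of the present window end and the last evaluable Hgb in the window.
2. For the treatment period, keep the start at Day 1 and state that the Day 1 baseline Hgb anchors the interpolation, although SAP 10.4.1.1 classes it as pre-treatment. Starting at the first evaluable value instead would drop the first 14 or 28 days for everyone; in the Week 20 example the result would be 85/127 = 67% (first value at Week 2) or 85/113 = 75% (Week 4), not 60%.
3. For the EP, start at the Week 24 visit date, or at the first evaluable Hgb in the EP if no earlier evaluable value allows interpolation back to Week 24.
4. Pre-specify a minimum covered span for the EP version, for example 7 days. Without it the headline case becomes 1/1 = 100%, which is no more informative than 3.4%. The 7 days is a choice, to be fixed before unblinding.
5. Use the same denominator for below, in, above, at least 13 g/dL and a rise of at least 1.0 g/dL.

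The cost is a short change to the SAP text and to the derivation code, with no new data. The downside is that a few participants with too short a covered span leave the EP version; their number should be reported by arm, because the exclusion depends on post-randomization missingness.
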